13.7 Sample Size Considerations

13.7.1 Statistical power for study analyses

The study will enroll 600 participants in total, including: 300 adults with AD, 100 non-AD adults, 150 children with AD, and 50 non-AD children. Of the 450 AD participants, approximately 390 will be dupilumab-naïve. Dupilumab-naïve participant enrollment will be targeted to achieve approximately two thirds moderate-to-severe participants (moderate-to-severe AD adults = 160, moderate-to-severe AD children = 80) and one third mild participants (mild AD adults = 100, mild AD children = 50). We will target approximately 60 long-term dupilumab participants who are currently being treated with dupilumab and have received dupilumab for ≥ 4 months (20 children, 40 adults). These long-term dupilumab participants will be excluded from the primary objective and secondary objective #1.

Based on these population targets, we make several additional assumptions regarding sizes for the study outcome groups. Among the dupilumab-naïve AD participants, only those who fail topical steroid treatment will initiate dupilumab treatment. Currently, we project a 50% failure rate for topical steroids among the dupilumab-naïve moderate-to-severe participants and a 5% failure for the dupilumab-naïve mild AD participants ([Brunner et al, 2016](#)). Therefore, we anticipate topical steroid non-response in 85 adult AD participants and 43 children with AD, who will go on to receive dupilumab. Finally, of these dupilumab-naïve participants who receive dupilumab

during the study, we expect that approximately 40% will achieve $EASI \leq 7$, per the following reference ([Beck et al, 2014](#)).

This sample size powers the primary comparison of type 2-high inflammation status by baseline severity group at 80%. Specific details about power and sample size for the primary and secondary objectives are below.

Power analysis for Primary Objective

The primary objective for the study is to determine if the type 2-high non-lesional skin (skin tape) endotype is associated with current mild versus moderate-to-severe AD disease.

[figure not shown]

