5.2 Secondary Estimands

The first of the two secondary estimands is the difference in mean gene expression from non-lesional skin tape transcriptome at Day 7, and separately at Day 168-224, between Non-AD vs. Mild DNAD and Non-AD vs. Moderate-to-severe DNAD children (6-17 years old), and separately adults (18+ year olds), enrolled in this study.

The second of the two secondary estimands is the mean change in normalized gene expression between Day 7 and Day 168-224 non-lesional skin tape transcriptomes, among topical steroid responders, dupilumab responders, dupilumab non-responders, non-AD, and long-term dupilumab responders in children (6-17 years old), and separately in adults (18+ year olds) enrolled in this study.

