To investigate changes in skin gene expression due to standard-of-care treatment as delineated in the protocol and how these changes may differ with study outcome groups (i.e., groups based on treatment regimen and response), we will model gene expression at both Day 7 and End of Study (Day 168-224) Visits using linear mixed models. Gene expression data will be normalized using the VST method. Models will include fixed effect variables for visit, study outcome group (topical steroid responders, dupilumab-naïve responders, dupilumab-naïve non-responders, non-AD, and long-term dupilumab participants), and visit x

study outcome group interaction, along with relevant covariates and a random intercept for each participant to account for pairing of Day 7 and End of Study samples. Among the covariates, there will be a binary variable that further distinguishes topical steroid responders who had mild AD to begin with since baseline (set covariate = 1) versus those who actually improved from having moderate-to-severe AD at baseline (set covariate = 0) in order to consider them as “true” topical steroid responders to compare with among the other outcome groups in the model (all remaining groups would set covariate = 0 as well). Using this model, we will examine responses to standard-of-care treatment as delineated in the protocol by contrasting Day 7 and End of Study Assessment Visits within outcome groups. We will also examine differences in response to standard-of-care treatment between any two outcome groups by testing the interaction term for visit effect in one outcome group versus another.

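### The SAP's mild-at-baseline indicator for secondary objective 2 has no visit interaction, so it does not deliver the comparison of true topical steroid responders that it was added for

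*SAP*

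**What the plan says.** SAP 9.2.2 sets out the mixed model for secondary objective 2. "Models will include fixed effect variables for visit, study outcome group", then the visit by "study outcome group interaction, along with relevant covariates and a random intercept for each participant". No other interaction is named for this model, either in the text or in the rows for models 1 to 22.

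The indicator is introduced as one of the covariates: "Among the covariates, there will be a binary variable that further distinguishes topical steroid responders who had mild AD to begin with since baseline". It is 1 for those participants and 0 for responders who were moderate-to-severe at baseline; "all remaining groups would set covariate = 0 as well". The stated aim is that the improvers serve as the true topical steroid responders when groups are compared.

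Two kinds of result are then taken from the model: "contrasting Day 7 and End of Study Assessment Visits within outcome groups", and between-group differences obtained by "testing the interaction term for visit effect in one outcome group versus another". SAP 5.2 defines the matching estimand as "the mean change in normalized gene expression between Day 7 and Day 168-224" by outcome group, and the footnote to the model table assigns it to models 1 and 12. SAP 6.2 defines a topical steroid responder as someone on topical steroid whose EASI never exceeds 7 by the 12 Week Steroid Assessment. It sets no condition on baseline severity.

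**The concern.** The indicator is meant to separate two kinds of responder in a comparison of changes over time. A variable that is fixed for each participant and enters only as a main effect describes differences in level, not in change. If the model is fitted as written, the topical steroid responder result remains an average over both kinds, while the text invites the reader to take it as the result for improvers.

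In the order of the SAP's list, the pairwise comparisons that involve topical steroid responders are numbers 1, 5, 6 and 7. These are models 2, 6, 7 and 8 in adults and 13, 17, 18 and 19 in children. Models 1 and 12 carry the estimand itself. A difference between steroid responders and dupilumab responders in these models could partly reflect the share of steroid responders who entered with mild disease.

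**Working it through.** **1. Why the indicator cancels.** For participant i in group g at visit v (0 = Day 7, 1 = End of Study), the model is

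Y(i,v) = a(g) + b(g)·v + γ·c(i) + u(i) + e(i,v),

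where c(i) is the indicator and u(i) the random intercept. The within-participant difference is

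Y(i,1) − Y(i,0) = b(g) + e(i,1) − e(i,0).

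Both γ·c(i) and u(i) drop out. With complete pairs the estimate of b(g) is the mean difference over everyone in the group, with or without the indicator.

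**2. Planned mix of responders.** Inputs from Protocol 13.7.1: 160 moderate-to-severe and 100 mild dupilumab-naïve adults; 80 and 50 children. For the moderate-to-severe stratum, "we project a 50% failure rate for topical steroids among" the dupilumab-naïve participants; for the mild stratum the projected failure rate is 5%.

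- Adults: 160 × 0.50 = 80, plus 100 × 0.95 = 95, total 175. Table 13.7.1.3 states 175.
- Children: 80 × 0.50 = 40, plus 50 × 0.95 = 47.5, total 87.5. The table states 87.
- Mild share: 95/175 = 47.5/87.5 = 54.3%.
- Sensitivity in adults: 42% to 68% for moderate-to-severe failure rates of 30-70% and mild failure rates of 0-20%.

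**3. What the model reports for adults.** The changes below are assumptions; neither document gives them. Improvers change by −1.0 throughout.

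| Change in mild-at-baseline responders | Planned contrast |
|---|---|
| 0 | (80 × −1.0 + 95 × 0)/175 = −0.46 |
| −0.5 | (80 × −1.0 + 95 × −0.5)/175 = −0.73 |
| −1.0 | −1.00 (no dilution) |

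The first row was checked by fitting the model to complete pairs, with dupilumab responders also changing by −1.0:

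| Model | Responder visit contrast | Difference in change from dupilumab responders |
|---|---|---|
| No indicator | −0.457 | +0.543 |
| Indicator as main effect | −0.457 (same standard error) | +0.543 |
| Indicator plus indicator × visit | −1.000 | 0.000 |

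Only the level moves. With assumed Day 7 levels of 2.0 (improvers) and 1.0 (mild), the fitted Day 7 level goes from (80 × 2.0 + 95 × 1.0)/175 = 1.46 without the indicator to 1.73 at indicator = 0. The true value for improvers is 2.0.

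**4. Incomplete pairs.** With equal dropout of 20% in both subgroups, the expected contrast is unchanged. With 30% dropout among improvers and 10% among mild responders, adding the main effect moves it from −0.439 to −0.415 (intraclass correlation 0.3) or from −0.415 to −0.404 (0.7). At 40% and 0% the largest move is from −0.421 to −0.370. Under unequal dropout each move was away from −1.0.

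**5. Power for the comparison that is wanted.** The entries of Table 13.7.1.3 are reproduced by

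fold change = exp{ √[ 2(z₁₋α/₂ + z₀.₈)² (1/10 + 0.4²)/n ] }, with two-sided α = 0.05/10,000.

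This gives 1.343 for n = 175 (stated 1.34) and 1.519 for n = 87 (stated 1.52); all 20 entries agree to rounding. For true responders:

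- Adults, n = 80: 1.55; with 20% dropout (n = 64): 1.63.
- Children, n = 40: 1.85; with 20% dropout (n = 32): 1.99.

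The standard error of the visit contrast rises by √(175/80) = 1.48.

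**The case against.** The strongest reply is that the blend is exactly what the SAP defines. Sections 5.2 and 6.2 ask for the mean change among topical steroid responders and set no baseline-severity condition, so models 1 and 12 estimate their declared target. That stands. A reader might infer that the estimand is biased; the documents do not support this. The failure is against the purpose given in 9.2.2.

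Other stronger readings also go too far.

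- *Mild participants could not become responders.* SAP 6.2 lets them, the protocol projects that 5% will fail, and its inclusion criterion 12 requires active lesions at Baseline and Day 7, so they can improve within the mild range.
- *They were mild before any steroid.* Protocol 3.1 lets AD participants use prescribed topical steroid on non-target skin before Day 7. Only study-provided steroid had not yet been given.
- *The reported change will be less than half the true one.* This requires mild responders not to change at all, which no figure in the documents supports.
- *The indicator can never alter the contrast.* That is exact for complete pairs only.

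It can also be said that the SAP does not use the words main effect. The SAP does name interactions where it wants them, however, as with age group, so this is the plain reading. Finally, the end of 9.2.2 allows stratified repeats and a further model with a covariate interaction. A repeat restricted to indicator = 0 would give the wanted comparison. But that route is conditional, refers to the Section 8.2 covariates (where this indicator is not listed), and interacts the covariate with disease group, not visit.

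**Conclusion.** The point holds in limited form. With the terms as written, the indicator leaves the within-group changes and their between-group differences unchanged when pairs are complete, and moves them only slightly otherwise. The promised comparison of true responders is therefore not obtained from models 1, 2, 6-8, 12, 13 or 17-19.

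The algebra needs no assumption beyond the stated model. The 54% share is a planning projection that varies with the failure rates. The size of any dilution is unknown: it is proportional to the difference in change between the two subgroups and is zero if they change alike. The primary objective is not affected. This should be fixed before the analysis, because choosing the responder definition after seeing results would be a post hoc decision.

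**What to change.** In SAP 9.2.2, add indicator × visit alongside the indicator, or split topical steroid responders by baseline severity so that the outcome group has six levels. Take the true-responder visit contrast, and its interactions with the other groups, at indicator = 0 (or from the moderate-to-severe-at-baseline level). Carry this through the pairwise models listed above.

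Align SAP 5.2, and 6.2 if the group is split, by saying whether the estimand is the change in all responders, in true responders, or both, and which is primary for this objective. Add rows to Protocol Table 13.7.1.3 for about 80 adults and 40 children.

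No new data are needed. The cost is precision: a standard error about 1.5 times larger, and a detectable fold change of about 1.55 instead of 1.34 in adults and about 1.85 instead of 1.52 in children. If that is not acceptable, the alternative is to keep the blend, say so, and remove the statement that the indicator identifies true responders.

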9.2 Primary Analysis of Secondary Endpoints/Outcomes

9.2.1 *Determining how gene expression in the skin (skin tape) differs between non-AD participants and those with current mild or moderate-to-severe AD disease [SO #1]*

This analysis will utilize WTS data from non-lesional and lesional skin tape samples collected at the Day 7 and End of Study Assessment (Day 168-224) Visits. To investigate whether skin gene expression differs due to AD status and severity of disease at each time point, we will carry out single-gene differential expression (DE) analysis using negative-binomial generalized linear models (GLM) to compare expression between

participants in different disease severity groups (non-AD, mild AD, and moderate-to-severe AD), while accounting for covariates. To assess effects of AD status, we will compare AD vs. non-AD, mild AD vs. non-AD, and moderate-to-severe AD vs. non-AD. We will compare mild AD vs. moderate-to-severe AD to explicitly test for differences based on AD severity. For all comparisons above and throughout this SAP, the Benjamini-Hochberg (BH) method will be used to adjust p-values to control the false discovery rate (FDR) at 5%, which we will apply across all tests that fall under a specific hypothesis (e.g., when testing whether gene expression is associated with non-AD vs AD, we will apply an adjustment for all genes tested. A separate adjustment will be applied when testing whether gene expression is associated with mild vs moderate-to-severe AD.

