Although the above analyses will focus on non-lesional skin samples, which will be available for all participants, we will also examine differences in disease signatures between lesional and non-lesional skin in participants from whom we have both types of samples (AD participants only) using a linear mixed model. Variance stabilizing transformation (VST)-normalized gene expression (Love et al. 2014) will be used as the outcome and models will include fixed effects for skin type (lesional or non-lesional), disease severity (mild or moderate-to-severe), and skin type x disease severity interaction, along with a random intercept for each participant to account for pairing of lesional and non-lesional samples. The interaction term will allow us to explicitly test for different changes between mild and moderate-to-severe AD in lesional vs. non-lesional skin. Using this model, we will also be able to compare gene expression differences between disease groups within lesional skin. Note that each of the above models will be fit for each visit separately. The above models will also be fit separately for children and adults, after which we will fit a combined model using interaction terms with age group to identify severity changes that are shared and unique to age groups.

In total, there will be 22 distinct models:

Response	Population	Regressors	Model #
Single-gene differential expression from Non-lesional STS collected at Day 7	Adults (18+ year olds)	Non-AD vs. DNAD (all severity) at Day 7	1
		Non-AD vs Mild DNAD at Day 7	2*
		Non-AD vs Moderate-to-Severe DNAD at Day 7	3*
		Mild vs. Moderate-to-Severe DNAD at Day 7	4
	Children (6-17 year olds)	Non-AD vs. DNAD (all severity) at Day 7	5
		Non-AD vs Mild DNAD at Day 7	6*
		Non-AD vs Moderate-to-Severe DNAD at Day 7	7*
		Mild vs. Moderate-to-Severe DNAD at Day 7	8
Single-gene differential expression from Non-lesional STS collected at End of Study (Day 168-224)	Adults (18+ year olds)	Non-AD vs. DNAD (all severity) at End of Study	9
		Non-AD vs Mild DNAD at End of Study	10*
		Non-AD vs Moderate-to-Severe DNAD at End of Study	11*
		Mild vs. Moderate-to-Severe DNAD at End of Study	12
	Children (6-17 year olds)	Non-AD vs. DNAD (all severity) at End of Study	13
		Non-AD vs Mild DNAD at End of Study	14*
		Non-AD vs Moderate-to-Severe DNAD at End of Study	15*
		Mild vs. Moderate-to-Severe DNAD at End of Study	16

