As noted in Section 9.2.1, these analyses will focus on non-lesional skin samples. However, for each outcome group separately, we will also examine differences in response to standard-of-care treatment between lesional and non-lesional skin in participants from whom we have both types of samples (AD participants only) by fitting mixed models based on VST-normalized data that include a random intercept for each participant and fixed effect terms for skin type (lesional or non-lesional), visit, and skin type x visit interaction. Using these models, we will also be able to investigate gene expression responses to standard-of-care treatment for each outcome group within lesional skin. Note that for lesional skin, we will compare target skin sampled at End of Study that corresponds to the original lesional skin sampled in the target area at Day 7, even if the lesion has resolved over the course of treatment.

The above tests will be performed separately for children and adults. We will also fit a combined model, using interaction terms with age group, to identify changes with outcome group that are shared and unique to age groups.

In total, there will be 34 models:

Response	Population	Regression Analysis Group(s)	Group Comparisons	Model #
VST-normalized gene expression from Non-lesional STS collected at BOTH Day 7 AND End of Study	Adults	Topical Steroid Responders, Dupilumab Responders, Dupilumab Non-Responders, Non-AD, and Long-Term Dupilumab Responders	For the 5 analysis groups, Day 7 vs. End of Study Indicator, Interactions	1*
		
 1. Non-AD vs. Topical Steroid Responders 2. Non-AD vs. Dupilumab Responders 3. Non-AD vs. Dupilumab Non-Responders 4. Non-AD vs. Long-Term Dupilumab Responders 5. Topical Steroid Responders vs. Dupilumab Responders 6. Topical Steroid Responders vs. Dupilumab Non-Responders 7. Topical Steroid Responders vs. 	Between the select 2 groups, Day 7 vs. End of Study Indicator, Interaction	2-11

		Long-Term Dupilumab Responders 8. Dupilumab Responders vs. Dupilumab Non-Responders 9. Dupilumab Responders vs. Long-Term Dupilumab Responders 10. Dupilumab Non-Responders vs. Long-Term Dupilumab Responders		
	Children	Topical Steroid Responders, Dupilumab Responders, Dupilumab Non-Responders, Non-AD, and Long-term Dupilumab Responders	For the 5 outcome groups, Day 7 vs. End of Study Indicator, Interactions	12*

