		1. Non-AD vs. Topical Steroid Responders 2. Non-AD vs. Dupilumab Responders 3. Non-AD vs. Dupilumab Non-Responders 4. Non-AD vs. Long-Term Dupilumab Responders 5. Topical Steroid Responders vs. Dupilumab Responders 6. Topical Steroid Responders vs. Dupilumab Non-Responders 7. Topical Steroid Responders vs. Long-Term Dupilumab Responders 8. Dupilumab Responders vs. Dupilumab Non-Responders 9. Dupilumab Responders vs. Long-Term Dupilumab Responders 10. Dupilumab Non-Responders vs. Long-Term Dupilumab Responders	Between the select 2 outcome groups, Day 7 vs. End of Study Indicator, Interaction	13-22
VST-normalized gene expression from matching set of Non-lesional AND Lesional STS collected at BOTH Day 7 AND End of Study (for the same target area on the lesional skin)	Adults	Topical Steroid Responders	Non-lesional vs Lesional Indicator, Day 7 vs. End of Study Indicator, Interaction	23
		Dupilumab Responders	Non-lesional vs Lesional Indicator, Day 7 vs. End of Study Indicator, Interaction	24
		Dupilumab Non-Responders	Non-lesional vs Lesional Indicator, Day 7 vs. End of Study Indicator, Interaction	25
		Long-term Dupilumab Responders	Non-lesional vs Lesional Indicator, Day 7 vs. End of Study Indicator, Interaction	26
	Children	Topical Steroid Responders	Non-lesional vs Lesional Indicator, Day 7 vs. End of Study Indicator, Interaction	27
		Dupilumab Responders	Non-lesional vs Lesional Indicator, Day 7 vs. End of Study Indicator, Interaction	28
		Dupilumab Non-Responders	Non-lesional vs Lesional Indicator, Day 7 vs. End of Study Indicator,	29

			Interaction	
		Long-term Dupilumab Responders	Non-lesional vs Lesional Indicator, Day 7 vs. End of Study Indicator, Interaction	30
	Adults AND Children	Topical Steroid Responders	Non-lesional vs Lesional Indicator, Day 7 vs. End of Study Indicator, Adults vs. Children Indicator, Interactions	31
		Dupilumab Responders	Non-lesional vs Lesional Indicator, Day 7 vs. End of Study Indicator, Adults vs. Children Indicator, Interactions	32
		Dupilumab Non-Responders	Non-lesional vs Lesional Indicator, Day 7 vs. End of Study Indicator, Adults vs. Children Indicator, Interactions	33
		Long-term Dupilumab Responders	Non-lesional vs Lesional Indicator, Day 7 vs. End of Study Indicator, Adults vs. Children Indicator, Interactions	34

** Models 1 and 12 will evaluate the second of our secondary estimands that will directly answer the second of our secondary objectives. The remaining models serve as supportive analyses.*

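### SAP 9.2.2 Models 23-34 put four samples per participant under one random intercept, so the skin type x visit standard error is too large whenever participants differ in their skin-type contrast or visit change

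*SAP*

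**What the plan says.** SAP 9.2.2 compares treatment response in lesional and non-lesional skin "for each outcome group separately", by "fitting mixed models based on VST-normalized data that include a random intercept for each participant and fixed effect terms for skin type", visit and skin type x visit. The SAP table lists these as Models 23-34: 23-30 by age cohort, and 31-34 with adults and children combined. The response is expression from a "matching set of Non-lesional AND Lesional STS collected at BOTH Day 7 AND End of Study", so a participant who enters has all four samples. For lesional skin the comparison uses "target skin sampled at End of Study that corresponds to the original lesional skin sampled in the target area at Day 7", whether or not it has since cleared. The section also takes the lesional-skin response to treatment from these models.

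No other random effect, covariance structure or robust standard error is named. Elsewhere the single intercept handles one pairing of two samples: in the main SO2 models it is "a random intercept for each participant to account for pairing of Day 7 and End of Study samples", and in the SO1 skin-type models (SAP 9.2.1) it is "a random intercept for each participant to account for pairing of lesional and non-lesional samples". Only Models 1 and 12 evaluate the second secondary estimand; the SAP labels the rest supportive.

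Protocol 13.6.3 lists, among the SO2 hypotheses, whether change from Day 7 to end of study differs by skin type. That is the skin type x visit term.

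**The concern.** One random intercept makes all four samples from a participant equally correlated. That is adequate for a single pair. In a crossed 2 x 2 layout it assumes that the lesional-minus-non-lesional difference does not vary between people beyond residual noise, and that the change between visits does not either.

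Both kinds of variation are plausible here. Resampling the original lesional area can make two samples of one skin type more alike than samples of different types. Individual response to treatment can shift both skin types together between visits. When either variance is present, a one-intercept model puts it into the residual and spreads it evenly over all the within-participant tests.

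At stake is the power to find genes whose treatment response differs by skin type, in groups that Protocol Table 13.7.1.3 puts as low as 34 adults and 17 children (dupilumab responders, before dropout). The p-values for response within lesional skin are also affected, and they enter a Benjamini-Hochberg procedure at a 5% false discovery rate.

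**Working it through.** **Plan figures.** Neither document states a standard error, variance component or power for Models 23-34, so there is no figure to reproduce. Protocol Table 13.7.1.3 is the nearest. It covers start-to-end change within a group, not skin type x visit. With CV 0.4, 10 reads and alpha 0.05/10,000, all 20 of its fold changes reproduce (for example, n = 34 gives 1.952 against the stated 1.95).

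**Inputs.** The layout and random-effects structure come from SAP 9.2.2. The variances are assumptions, taken relative to Ve: Vs from 0 to 2 and Vv from 0 to 1.

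**Model for the data.** Expression = fixed effects + participant + participant-by-skin-type (Vs) + participant-by-visit (Vv) + residual (Ve), balanced 2 x 2 within participant.

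**True error terms (expected mean squares).**
- Skin type, averaged over visits: Ve + 2Vs
- Visit, averaged over skin types: Ve + 2Vv
- Skin type x visit: Ve

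**Error the planned model uses for all three.** The average of these: [(Ve + 2Vs) + (Ve + 2Vv) + Ve]/3 = Ve + (2/3)(Vs + Vv).

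**Ratio of model SE to true SE**, with P = Ve + (2/3)(Vs + Vv):
- Interaction: sqrt(P/Ve), above 1 whenever Vs or Vv exceeds 0.
- Averaged skin type: sqrt[P/(Ve + 2Vs)], below 1 only if Vs > Vv/2.
- Averaged visit: sqrt[P/(Ve + 2Vv)], below 1 only if Vv > Vs/2.
- Visit within lesional skin (true variance 2(Ve + Vv), modelled 2P): sqrt[P/(Ve + Vv)], above 1 if Vs > Vv/2 and below 1 if Vs < Vv/2.
- Skin type at Day 7, which is the skin-type coefficient under reference coding: sqrt[P/(Ve + Vs)], below 1 only if Vs > 2Vv.

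**Results.** SE ratios, with simulated type I error at nominal 5% in brackets (20,000 simulated data sets of 34 participants per row):

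| Vs/Ve, Vv/Ve | P/Ve | Interaction | Visit in lesional skin | Skin type (avg) | Visit (avg) |
|---|---|---|---|---|---|
| 0, 0 | 1.00 | 1.00 (5.1%) | 1.00 (5.3%) | 1.00 (4.8%) | 1.00 (5.2%) |
| 0.5, 0 | 1.33 | 1.15 (2.5%) | 1.15 (2.7%) | 0.82 (11%) | 1.15 (2.6%) |
| 1, 0 | 1.67 | 1.29 (1.2%) | 1.29 (1.2%) | 0.75 (14%) | 1.29 (1.3%) |
| 0, 1 | 1.67 | 1.29 (1.2%) | 0.91 (7.6%) | 1.29 (1.3%) | 0.75 (14%) |
| 0.5, 1 | 2.00 | 1.41 (0.6%) | 1.00 (5.2%) | 1.00 (5.0%) | 0.82 (11%) |
| 1, 1 | 2.33 | 1.53 (0.4%) | 1.08 (3.6%) | 0.88 (8.4%) | 0.88 (8.6%) |
| 2, 0.5 | 2.67 | 1.63 (0.2%) | 1.33 (1.2%) | 0.73 (15%) | 1.15 (2.7%) |

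REML fits of the planned model to 150 simulated data sets at each of (1, 0), (0, 1) and (1, 1) gave interaction ratios of 1.33, 1.32 and 1.46, in line with the formula.

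**Power of the interaction test.** Take an effect with 80% power under the correct error, two-sided 5%. With SE ratio r, power is Phi(1.960 + 0.842 - 1.960r):
- r = sqrt(4/3) = 1.155: Phi(0.538) = 70.5%
- r = sqrt(5/3) = 1.291: Phi(0.271) = 60.7%
- r = sqrt(7/3) = 1.528: Phi(-0.192) = 42.4%

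The loss grows at a stricter per-gene threshold, because the penalty is the critical value times (r - 1).

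**The case against.** Four points on the other side carry weight.

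- **The models are supportive.** The SO2 estimand (SAP 5.2) is non-lesional only. Models 1 and 12, which evaluate it, have two samples per participant, where one intercept suffices. This stands and limits the weight of the point.
- **The size is unknown.** No variance component is documented; with Vs = Vv = 0 the planned model is exact. Resampling of the same area is stated for lesional skin only, and the lesion may have resolved. This also stands, so the percentages are illustrations.
- **A conservative interaction test creates no false positives.** True, but it is the test of a listed hypothesis in small groups. The lesional visit test can err the other way if Vv is more than twice Vs.
- **Protocol 13.4.3 plans the SO2 tests separately for lesional and non-lesional skin**, with two samples per participant. Such a lesional-only model would be sound. But the SAP table lists none and takes the lesional response from the four-sample models.

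A reader might go further and infer that the lesional vs non-lesional test has standard errors that are too small, so that its 5% false discovery rate fails. The documents do not support that as a general statement. It needs Vs > Vv/2 for the averaged effect, or Vs > 2Vv for the Day 7 coefficient, and setting Vv to zero is a strong assumption in a study of treatment response. At Vs = 0.5Ve and Vv = Ve the averaged skin-type test is exact. Protocol 13.6.3 also lists no lesional vs non-lesional main effect among the SO2 hypotheses.

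**Conclusion.** The random-effects structure of Models 23-34 is too simple for the four-sample layout. The skin type x visit standard error is too large if either participant-by-skin-type or participant-by-visit variance is present, whichever dominates: 1.15 to 1.63 times the true value over the non-zero combinations tried. Whenever one of them is non-zero, at least one of the two averaged main-effect tests is also anti-conservative, but which one cannot be told from the documents. For response within lesional skin, which SAP 9.2.2 does ask for, the ratio ran from 0.91 to 1.33.

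These figures rest on assumed variances and on balanced data, which the matched-set requirement makes reasonable. The point should be corrected because the remedy is cheap and a listed hypothesis depends on it. It does not call the SO2 estimand analysis into question.

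**What to change.** In SAP 9.2.2, for Models 23-34, replace the single intercept with (1|participant) + (1|participant:skin type) + (1|participant:visit), and drop a term for genes where it is estimated at zero. All components are identifiable from four samples per participant, and each test then has its own error term.

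Both added terms are needed. With participant-by-skin-type alone at Vs = Vv = Ve, the residual averages the visit and interaction mean squares, (3 + 1)/2 = 2. The interaction SE stays sqrt(2) = 1.41 times the true value. The averaged visit ratio falls from 0.88 to sqrt(2/3) = 0.82, and its type I error rises from about 8% to 11%.

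Either of two alternatives would also serve:
- an unstructured 4 x 4 within-participant covariance, which has 4 x 5/2 = 10 parameters and so is demanding for a group of 17;
- testing the interaction on each participant's difference of differences, and the lesional response on paired lesional differences.

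The cost is one line in the SAP, slightly more computing and some singular fits in small groups. The interaction would also have n - 1 rather than 3(n - 1) error degrees of freedom. Models 1-22 need no change.
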